## 1) Protocol Title

The effect of topical botulinum toxin eyedrop on palpebral fissure height, ocular surface and tearing.

## 2) Objectives

Aim 1: To determine the effect of botulinum toxin eyedrop on palpebral fissure height.

Aim 2: To determine the effect of botulinum toxin eyedrop on ocular surface.

Aim 3: To determine the effect of botulinum toxin eyedrop on tearing of the eye.

Hypothesis: We hypothesize that the application of a botulinum toxin (BT) eyedrop will cause a decrease in subjects' palpebral fissure height, improve ocular surface disease, and decrease reflexive tearing in patients with dry eyes.

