## 3) Background

BT is a neurotoxin produced by the bacterium Clostridium botulinum and related species. (1) It prevents release of acetylcholine, a neurotransmitter from axons ending at the neuromuscular junction, causing paralysis.(2) [name] used the first documented therapeutic application of BT when he used it for strabismus by injecting it into the extraocular muscles.(4) In 1989, BT was licensed by the U.S. Food and Drug Administration for treatment of strabismus.(4) Since then, there has been massive research on BT, which has led to the addition of newer formulations with a large range of indications. To date, BT has been widely used by neurologists and cosmetic practitioners. Recently, urologists and pain specialists are increasingly using BT for various indications. Nevertheless, neurological disorders are the most common therapeutic indication of BT. (5)

The seven main types of BT are type A to G (A, B, C1, C2, D, E, F and G).(6) Types A and B can cause disease in humans but are also used for therapeutic and cosmetic etiologies.(7) The effect of BT-A on shaping the eyebrow was first reported in 1989.(8) BT injections for facial wrinkles is the most frequently performed cosmetic procedure in the United States. BT is used for the treatment of frown lines, forehead lines, and crow's feet, which are the cosmetic indications approved by the FDA. (9)

BT has a broad margin of safety (lethal dose 50% (LD50)) in humans that can reach up to 40 U/kg BW. Therefore, its cosmetic use is relatively safe. BT does not cause any long-term adverse or side effects or persistent changes at the nerve terminals and targeted muscles. (10) Some known adverse effects for BT injection use include eyelid ptosis and weakness of the muscles. Rare complications of BT injection use include dysphagia, botulism, and possibly death, usually seen in patients treated for non-cosmetic issues. (11)

Graves' ophthalmopathy (GO) or thyroid eye disease is a potentially sight-threatening ocular disease that has puzzled physicians and scientists for nearly two centuries, usually occurring in patients with hyperthyroidism or a history of hyperthyroidism.(12) The most common clinical sign of GO is upper eyelid retraction, occurring to a various extent in about 90% of the patients suffering from GO.(13) It may cause cosmetic complaints as well as functional problems due to, for example, exposure keratitis.

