Surgical correction may be performed because of corneal exposure at any time during the disease, cosmetic rehabilitation usually after the disease is inactive and after other interventions such as orbital decompression or strabismus surgery are done. (14) During the active phase of the disease, it's better not to do any surgery, although patients with severe lid retraction may suffer from keratitis during this long period of exposure. Some alternatives for surgery to treat thyroid lid retraction have been postulated, such as, local guanethidine, but it was not used due to adverse side effects.(15) In another study, somatostatin or prednisolone were used for eyelid retraction; however, there was little effect in the palpebral fissure height.(16) Several reports illustrated the effects of injections with BT in thyroid lid retraction; (17-20) In some studies BT injection was done through the skin with 5-6 units in the eyelid (21, 22). In other studies injections were done through the conjunctiva with upper eyelid eversion (23, 24) with up to 10 units of BT. Some adverse effects of BT injections are entropion, ectropion, epiphora, photophobia, diplopia and ecchymosis. (25)

The purpose of this study is to see simply if eyelid position changes with a drop of BT in the eye, removing the stress and discomfort of any injections, especially important in non-cooperative patients since there have been no studies of such kind.

BT injection into the lacrimal gland has been also used to treat epiphora in patients with aberrant regeneration after 7th nerve palsy leading to crocodile tears. (26, 27). The effects of topical BT have not been studied on tear production. In our study we will use Schirmer's I test with topical anesthesia and tear meniscus height (27) to see the effect on tear production at different intervals. Also tear break up time (TBUT) and corneal fluorescein staining will be used to evaluate the ocular surface.

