#### 4) Inclusion and Exclusion Criteria\*

##### **Inclusion Criteria**

- Adults aged 18 and above that present to the oculoplastic and reconstructive surgery department that are able to provide informed consent to participate
- Presence of upper eyelid retraction or asymmetry( >1mm)

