##### **Exclusion Criteria**

- Adults unable to consent
- Individuals less than 18 years of age
- Prisoners
- Pregnant women.
  - o Patients will be asked if they are pregnant by research staff before participation in the study.
- Women who are breast-feeding
- Known contradictions or sensitivities to study medication
- Grossly abnormal lid margins, anatomical abnormalities
- Variable ptosis or eyelid position (e.g., myasthenia gravis, blepharospasm)
- Any ocular or systemic condition that, in the opinion of the investigator, would confound study data, interfere with the subject's study participation, or affected the subject's safety or trial parameters
- Presence of an active ocular infection
- Inability to sit comfortably for 15 – 30 minutes
- Botulinum toxin injection in the eyelids during the past 3 weeks.
- Neuromuscular disorders (e.g., Parkinson's disease or myasthenia gravis)
- Medication use known to interfere with the effects of BTX-A within the previous 1 month (e.g., aminoglycoside or benzodiazepines),
- Previous history of hypersensitivity reactions to BTX-A
- Dysfunction of tear production or secretion (e.g., meibomian gland dysfunction or Sjogren's syndrome),

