Outcome Measure Description: Scoring of ocular surface and tearing will be done by fluorescein staining with a slit lamp and Schirmer I test with anesthesia.

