### **Data Analysis**

Statistical analysis will be performed by the Oculoplastic Research Laboratory research fellow. A paired t-test will be used to analyze the difference in palpebral fissure height, ocular surface and tearing. 34 subjects will be required to perform perimetric statistics.

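### The only planned test is a paired t-test, so no stated analysis compares the randomised botulinum toxin and saline arms on the primary or the secondary outcomes

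*Combined protocol and SAP*

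**What the plan says.** **Analysis.** The Data Analysis section states: "A paired t-test will be used to analyze the difference in palpebral fissure height, ocular surface and tearing". It names no other test and does not say what is paired with what.

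**Design.** Section 5 (Procedures Involved) and Number of Subjects plan 34 patients, 17 on BT and 17 on saline, for alpha 0.05 and 80% power. Section 5 treats one eye per patient, the one with the larger palpebral fissure height. The later Procedures Involved section schedules five follow-up visits. Its Part 4 describes the data as measurements before and after treatment, and blinds the analyst to which eye was treated.

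**First 10 patients.** Section 5 and Part 2 of the later Procedures Involved section give BT to the first 10 patients for a futility look, before randomisation. Section 5 then speaks of 34 patients in total, and Study Timelines ends the study at 34 recruited.

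**Hypothesis.** Section 2 (Objectives) predicts that the drop will "decrease reflexive tearing in patients with dry eyes". Aim 3 in the same section refers only to tearing of the eye. The inclusion criteria ask for "Presence of upper eyelid retraction or asymmetry( >1mm" (in mm), adult age and consent. The exclusion criteria remove "Dysfunction of tear production or secretion (e.g., meibomian gland dysfunction" and similar conditions. The secondary outcomes are scored by "fluorescein staining with a slit lamp and Schirmer I test with anesthesia".

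**The concern.** A randomised saline arm is there to remove whatever would have happened without the active drug: drift over time, repeat testing, and the expectations of patients and assessors. A paired test leaves it out. A before-after test in the BT arm asks whether BT patients changed, not whether they changed more than saline patients. Any change common to both arms is then credited to BT.

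The defect reaches the primary outcome, because the sentence on the paired test lists palpebral fissure height first. At stake is whether the trial can support any statement about BT against placebo.

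The hypothesis wording is a separate and smaller matter. It concerns what a tearing result could be said to apply to.

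**Working it through.** **1. The plan's own figure.** The 17 per group cannot be reproduced, because no effect size or SD is given. Solving backwards for a two-sample t-test with 17 per arm, two-sided 0.05 (sidedness is not stated, so this is assumed) and 80% power:
- noncentral t, 32 df, noncentrality d/√(2/17): d = 0.99 SD;
- normal approximation: (1.960 + 0.842) × √(2/17) = 2.802 × 0.343 = 0.96 SD.

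An assumed difference of 1.0 SD needs exactly 17 per arm with the t-test (power 80.7%). The stated size is therefore compatible with a between-arm comparison of a large effect, but the documents do not confirm that this is its origin.

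**2. Which pairings are possible.**
- *Before versus after:* favoured by Part 4 of the later Procedures Involved section. It uses one arm at a time, or both pooled.
- *Treated versus fellow eye:* possible, since the analyst is blinded to the treated eye. The treated eye is chosen as the wider one, not by lot, and the contrast is with an untreated eye, not with saline.
- *BT versus saline patient:* would need matched patients, and no matching is described.

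Neither of the first two compares the randomised arms.

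**3. False attribution under before-after pairing.** Inputs from the plan: n = 17 per arm, alpha 0.05. Assumptions: two-sided test, normal change scores, no BT-saline difference, and the same mean change d in both arms, in SDs of the change. For one arm, t has 16 df, critical value 2.120 and noncentrality d√17. Pooling all 34 patients gives 33 df and d√34. With p the probability of significance in one arm, the probability of a significant BT arm and a non-significant saline arm is p(1 − p).

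| Common change d | d√17 | BT arm significant, p | BT significant, saline not, p(1 − p) | Pooled 34 significant |
|---|---|---|---|---|
| 0 | 0 | 5% | 5% | 5% |
| 0.25 | 1.03 | 16% | 14% | 29% |
| 0.5 | 2.06 | 49% | 25% | 81% |
| 0.75 | 3.09 | 83% | 14% | 99% |

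A two-sample test on change stays at 5% in every row. Simulated ANCOVA with baseline as covariate (20,000 trials per row, assumed correlation 0.5) gives 4.7% to 5.1%. For a staining score the normal model is only an approximation.

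**4. What a between-arm test can detect** (17 vs 17, 80% power, two-sided 0.05):
- follow-up values alone: 0.99 SD;
- ANCOVA (31 df), 0.992 × √(1 − r²), for an assumed baseline-to-follow-up correlation r: 0.95 SD at r = 0.3, 0.86 at 0.5, 0.71 at 0.7.

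For comparison, a paired test on 17 patients reaches 80% power at 0.72 SD of the change. An unadjusted between-arm test on change needs 0.99 SD of the change.

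**5. The first 10 patients.** If they count toward the 17 on BT, 17 − 10 = 7 BT patients are randomised. With 7 vs 17 the unadjusted detectable difference is 1.32 SD (noncentral t, 22 df, noncentrality d/√(1/7 + 1/17)). The normal approximation is 2.802 × 0.449 = 1.26 SD. The figures in step 4 would then not apply to the randomised comparison.

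**6. Hypothesis wording.** No eligibility criterion defines dry eye, and the exclusion of tear dysfunction removes part of that population. Section 3 (Background) describes the Schirmer test and tear meniscus height as used "to see the effect on tear production at different intervals". No outcome is defined as reflex tearing.

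**The case against.** The design is randomised, placebo-controlled and blinded, with equal arms sized for stated power. A fair reader may say that a comparison of arms is plainly intended and that the test is loosely named. That is plausible, but the section that fixes the analysis would still be carried out as paired tests. Someone who follows it has no instruction to use the saline arm.

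A second objection stands in part. With treated-versus-fellow-eye pairing, changes shared by both eyes cancel, so the 16%, 49% and 83% figures do not apply. They hold only for before-after pairing. Under either reading, though, BT is not compared with saline.

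A third also stands. A between-arm test detects only larger effects, and its validity depends on who counts as randomised. That argues for settling the count, not for keeping the paired test. For the first 10 patients, who have no control, a paired test is usable.

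On the hypothesis, a reader might infer that dry-eye patients are barred altogether, or that the Schirmer test with anesthesia cannot capture reflex tearing. The documents support neither. Section 3 notes that lid retraction can cause "functional problems due to, for example, exposure keratitis", so exposure-related dryness may well be enrolled. What anesthesia does to reflex tearing is not stated in the plan. Aim 3 already refers to tearing in general, so only the hypothesis sentence is out of line.

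**Conclusion.** The analysis is wrong as written: no stated test compares the randomised arms, for palpebral fissure height or for ocular surface and tearing. With before-after pairing, a common change of 0.25 to 0.75 SD would make the BT arm significant in 16% to 83% of trials in which BT adds nothing to saline. A between-arm test would stay near 5%. These rates rest on two-sided testing, 17 BT patients, normal change scores and assumed sizes of common change, since the documents give no SD or expected change.

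Two further inferences should be avoided. The rates show what could happen, not that a common change will occur. And the documents do not establish that the first 10 patients are counted in the 34. They leave it open, which is why it must be settled.

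The hypothesis mismatch is real but is a matter of wording. It affects the secondary claim on tearing and not the primary outcome.

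**What to change.** 1. **Data Analysis.** Replace the paired t-test with a comparison of BT and saline adjusted for the baseline value (ANCOVA), for palpebral fissure height, Schirmer result and staining score, at one of the five follow-up visits named in advance. State whether testing is two-sided. Keep paired before-after results as description within each arm and for the first 10 BT-only patients.
2. **First 10 patients.** Restrict the between-arm comparison to randomised patients. Reconcile section 5, Number of Subjects, Study Timelines and Part 2 of the later Procedures Involved section on whether these 10 count toward the 34, and restate the randomised number per arm.
3. **Objectives.** Reword the hypothesis to match Aim 3 and the enrolled population, dropping the references to reflex tearing and dry eyes.

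**Cost.** A few sentences and a little more analysis work. Baseline values are already collected, so no new measurement is needed. No new patients are needed if 17 per arm are in fact randomised; if the 10 are inside the 34, the sponsor must either accept less power or recruit more. The between-arm test also detects only larger effects than the paired test: about 0.99 SD unadjusted, against 0.72 SD with 17 pairs.

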## 3) Background

BT is a neurotoxin produced by the bacterium Clostridium botulinum and related species. (1) It prevents release of acetylcholine, a neurotransmitter from axons ending at the neuromuscular junction, causing paralysis.(2) [name] used the first documented therapeutic application of BT when he used it for strabismus by injecting it into the extraocular muscles.(4) In 1989, BT was licensed by the U.S. Food and Drug Administration for treatment of strabismus.(4) Since then, there has been massive research on BT, which has led to the addition of newer formulations with a large range of indications. To date, BT has been widely used by neurologists and cosmetic practitioners. Recently, urologists and pain specialists are increasingly using BT for various indications. Nevertheless, neurological disorders are the most common therapeutic indication of BT. (5)

The seven main types of BT are type A to G (A, B, C1, C2, D, E, F and G).(6) Types A and B can cause disease in humans but are also used for therapeutic and cosmetic etiologies.(7) The effect of BT-A on shaping the eyebrow was first reported in 1989.(8) BT injections for facial wrinkles is the most frequently performed cosmetic procedure in the United States. BT is used for the treatment of frown lines, forehead lines, and crow's feet, which are the cosmetic indications approved by the FDA. (9)

BT has a broad margin of safety (lethal dose 50% (LD50)) in humans that can reach up to 40 U/kg BW. Therefore, its cosmetic use is relatively safe. BT does not cause any long-term adverse or side effects or persistent changes at the nerve terminals and targeted muscles. (10) Some known adverse effects for BT injection use include eyelid ptosis and weakness of the muscles. Rare complications of BT injection use include dysphagia, botulism, and possibly death, usually seen in patients treated for non-cosmetic issues. (11)

Graves' ophthalmopathy (GO) or thyroid eye disease is a potentially sight-threatening ocular disease that has puzzled physicians and scientists for nearly two centuries, usually occurring in patients with hyperthyroidism or a history of hyperthyroidism.(12) The most common clinical sign of GO is upper eyelid retraction, occurring to a various extent in about 90% of the patients suffering from GO.(13) It may cause cosmetic complaints as well as functional problems due to, for example, exposure keratitis.

Surgical correction may be performed because of corneal exposure at any time during the disease, cosmetic rehabilitation usually after the disease is inactive and after other interventions such as orbital decompression or strabismus surgery are done. (14) During the active phase of the disease, it's better not to do any surgery, although patients with severe lid retraction may suffer from keratitis during this long period of exposure. Some alternatives for surgery to treat thyroid lid retraction have been postulated, such as, local guanethidine, but it was not used due to adverse side effects.(15) In another study, somatostatin or prednisolone were used for eyelid retraction; however, there was little effect in the palpebral fissure height.(16) Several reports illustrated the effects of injections with BT in thyroid lid retraction; (17-20) In some studies BT injection was done through the skin with 5-6 units in the eyelid (21, 22). In other studies injections were done through the conjunctiva with upper eyelid eversion (23, 24) with up to 10 units of BT. Some adverse effects of BT injections are entropion, ectropion, epiphora, photophobia, diplopia and ecchymosis. (25)

The purpose of this study is to see simply if eyelid position changes with a drop of BT in the eye, removing the stress and discomfort of any injections, especially important in non-cooperative patients since there have been no studies of such kind.

BT injection into the lacrimal gland has been also used to treat epiphora in patients with aberrant regeneration after 7th nerve palsy leading to crocodile tears. (26, 27). The effects of topical BT have not been studied on tear production. In our study we will use Schirmer's I test with topical anesthesia and tear meniscus height (27) to see the effect on tear production at different intervals. Also tear break up time (TBUT) and corneal fluorescein staining will be used to evaluate the ocular surface.

#### 4) Inclusion and Exclusion Criteria\*

##### **Inclusion Criteria**

- Adults aged 18 and above that present to the oculoplastic and reconstructive surgery department that are able to provide informed consent to participate
- Presence of upper eyelid retraction or asymmetry( >1mm)

##### **Exclusion Criteria**

- Adults unable to consent
- Individuals less than 18 years of age
- Prisoners
- Pregnant women.
  - o Patients will be asked if they are pregnant by research staff before participation in the study.
- Women who are breast-feeding
- Known contradictions or sensitivities to study medication
- Grossly abnormal lid margins, anatomical abnormalities
- Variable ptosis or eyelid position (e.g., myasthenia gravis, blepharospasm)
- Any ocular or systemic condition that, in the opinion of the investigator, would confound study data, interfere with the subject's study participation, or affected the subject's safety or trial parameters
- Presence of an active ocular infection
- Inability to sit comfortably for 15 – 30 minutes
- Botulinum toxin injection in the eyelids during the past 3 weeks.
- Neuromuscular disorders (e.g., Parkinson's disease or myasthenia gravis)
- Medication use known to interfere with the effects of BTX-A within the previous 1 month (e.g., aminoglycoside or benzodiazepines),
- Previous history of hypersensitivity reactions to BTX-A
- Dysfunction of tear production or secretion (e.g., meibomian gland dysfunction or Sjogren's syndrome),

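### The hypothesis predicts better ocular surfaces, but entry requires no staining and tear dysfunction is excluded, so an unknown share of eyes at the floor dilutes the staining result

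*Combined protocol and SAP*

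**What the plan says.** All references are to the combined protocol and SAP.

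- **Section 2, Objectives.** Aim 2 has no direction: "To determine the effect of botulinum toxin eyedrop on ocular surface". The direction is in the Hypothesis sentence, which predicts that the drop will "improve ocular surface disease, and decrease reflexive tearing in patients with dry eyes".
- **Section 4, Inclusion Criteria.** Apart from age, clinic attendance and ability to consent, the only condition is "Presence of upper eyelid retraction or asymmetry( >1mm"). No minimum staining, tear break-up time or Schirmer value is set.
- **Section 4, Exclusion Criteria.** Patients with "Dysfunction of tear production or secretion" are excluded; meibomian gland dysfunction and Sjogren's syndrome are the examples given.
- **Section 3, Background.** Exposure damage is expected in some patients with retraction: "patients with severe lid retraction may suffer from keratitis during this long period of exposure". Exposure keratitis is not excluded by name.
- **Procedures Involved, Outcomes Measures.** The secondary outcome reads: "Scoring of ocular surface and tearing will be done by fluorescein staining with a slit lamp and Schirmer I test with anesthesia". No staining scale, range or baseline threshold is given.
- **Data Analysis.** A paired t-test is named for fissure height, ocular surface and tearing. No comparison between arms is described, and nothing is said about eyes that start at zero.

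**The concern.** The hypothesis predicts improvement of a condition that patients need not have at entry, and the exclusions remove recognised causes of it. An eye with no staining at baseline can only stay at zero or get worse. Every such eye adds nothing to a measured improvement, and the number of them is left to chance.

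Two readings of the results are at stake. A null staining result in all patients could be reported as no effect on the ocular surface when part of the sample had no room to improve. And for an eye at zero, the only change the score can register is new staining, which the secondary outcome does not mention. The reference to dry eyes adds a further mismatch, because the exclusion of tear dysfunction removes patients whom a reader would expect that phrase to cover.

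**Working it through.** **1. The plan's own figure.** Number of Subjects gives 17 per group (34 in total) for alpha 0.05 and 80% power, without endpoint, effect size, standard deviation or sidedness. It can therefore be neither confirmed nor refuted. Solved backwards for a two-sided comparison of two means, the standardised difference is (1.960 + 0.842) × √(2/17) = 0.96, or 0.99 with the t distribution.

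**2. How many stained eyes a perfect drug needs.** Assume that toxin clears every stained eye, that saline clears none, and that all stained eyes share one grade, scored 1. With k stained toxin eyes out of 17, the mean improvement is k/17 and its variance is (17/16)(k/17)(1 − k/17).

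For k = 4:
- mean = 4/17 = 0.235
- SD = √(1.0625 × 0.235 × 0.765) = 0.437
- SE = 0.437/√17 = 0.106
- t = 0.235/0.106 = 2.22

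On 16 degrees of freedom (paired test within the toxin arm) p = 0.041. In the two-sample test every saline change is zero, so the pooled SE is the same 0.106; on 32 degrees of freedom p = 0.034. Fisher's exact test compares cleared with not cleared, k/17 against 0/17.

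| Stained toxin eyes (k) | Paired t | Two-sample t | Fisher, two-sided |
|---|---|---|---|
| 3 | 0.083 | 0.073 | 0.227 |
| 4 | 0.041 | 0.034 | 0.103 |
| 5 | 0.020 | 0.015 | 0.044 |

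The requirement is 4 of 17 under a t-test and 5 of 17 under Fisher's test.

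**3. The chance of enrolling that many.** The document gives no prevalence of staining, so 20%, 30% and 40% are assumptions. The number of stained toxin eyes is taken as Binomial(17, p).

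| Assumed prevalence | Expected stained of 17 | P(4 or more), t-test | P(5 or more), Fisher |
|---|---|---|---|
| 20% | 3.4 | 45% | 24% |
| 30% | 5.1 | 80% | 61% |
| 40% | 6.8 | 95% | 87% |

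A drug that clears only some eyes, or a saline arm in which some eyes clear, would do worse under either test. If grades vary between stained eyes, the t-test needs somewhat more than the shared-grade case suggests.

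**4. Cross-check on mean change.** Let a share f of patients be at the floor, and set the effect in the others to the value that 17 per arm detects with 80% power. With constant SD the average effect is 0.99 × (1 − f). Simulation (40,000 runs, two-sample t-test) gives two further cases: floor eyes fixed at no change, and floor eyes able only to worsen. In the last case saline eyes at the floor may worsen while toxin eyes mostly do not, so part of the power comes from prevented worsening.

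| f (assumed) | Constant SD | Floor change fixed at 0 | Floor can only worsen |
|---|---|---|---|
| 25% | 56% | 63% | 68% |
| 50% | 29% | 43% | 57% |
| 75% | about 11% | 18% | 49% |

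Both approaches agree: power falls as the floor share grows, by an amount that depends on the model, but it does not vanish.

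**The case against.** A reader might infer that improvement cannot be shown at all, or that many patients will start at zero. Neither is supported. Background says that retraction can cause keratitis, such patients remain eligible, and the treated eye is the one with the larger fissure, where exposure is plausibly greater. The calculation itself gives a perfect drug a good chance of success at 30% or 40% prevalence. The share at the floor is simply not documented.

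Other points on that side also have weight:

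- **Aim 2 is neutral.** The prediction sits only in the Hypothesis sentence. In that sentence, dry eyes may qualify only the reflexive tearing. This limits the point to the hypothesis but does not remove the need to reconcile it.
- **Harm has a possible home.** The definition under Adverse Events and Serious Adverse Events covers new events and existing ones that worsen. Clinically relevant new staining could fall under it, so it would be wrong to say that the plan has no route to report it. Staining is not named there, however.
- **Tear break-up time.** Background lists it as a second measure of the ocular surface, and it can improve in an eye without staining. It is missing from the measurement lists and from the secondary outcome, so it does not rescue the staining result.
- **The exclusion is defensible.** Removing meibomian gland dysfunction and Sjogren's syndrome removes staining unrelated to lid exposure. That is a reason to change the hypothesis, not the exclusion.
- **Fisher's test is not the planned test.** This stands. The 5 of 17 threshold depends on that test, and the t-test threshold of 4 is closer to the plan.

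**Conclusion.** The point holds as dilution, not impossibility. The Hypothesis and the eligibility criteria do not describe the same patients, eyes at zero staining cannot improve on the score, and the planned analysis makes no allowance for them. Even with a perfect drug, the chance of enough stained toxin eyes runs from 45% to 95% under a t-test (24% to 87% under Fisher's test) across assumed prevalences of 20% to 40%. If half the patients were at the floor, power of 80% would fall to between 29% and 57%, depending on the model.

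These figures rest on assumed prevalences, on a single shared grade in the first calculation, and on an assumed effect size in the second. They show how sensitive the result is and do not predict it. Ocular surface is a secondary outcome, so the primary outcome of palpebral fissure height is untouched.

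**What to change.** 1. Reconcile the Hypothesis in section 2 with the tear-dysfunction exclusion in section 4, so that it no longer refers to dry-eye patients whom the trial excludes. Keep Aim 2 neutral.
2. In Data Analysis, compare change in staining between the randomised arms in all patients and in both directions.
3. Report new or increased staining by arm under the existing adverse-event definition, and name staining there.
4. Limit any claim of improvement to eyes with staining above zero at baseline, and give their number in each arm.
5. State in advance that a null result in all patients will not be read as no effect on the ocular surface.

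The data are already to be collected before treatment and at every visit, so the cost is wording and analysis only. The price is a narrower secondary claim and a small subset: at the assumed prevalences, about 3 to 7 stained eyes per arm (17 × 0.2 = 3.4 to 17 × 0.4 = 6.8). Results in that subset would be descriptive more than confirmatory. Enrolment does not change.
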